8.7 Quality Control

These steps provide a measure of consistency of image analysis.

- 1) The Mindray DC 7 Digital Diagnostics Ultrasound System - To monitor operation of Mindray DC 7 Digital Diagnostics Ultrasound System, a precision small parts grey scale phantom (RMI 404 GS LE, Small Parts Gray Scale-Attenuation coefficients of 0.7 db/cm/MHz) simulating the lumen-intima and media-adventitia boundaries is scanned every 6 months. The distance between vertical and horizontal targets is measured with our IMT assessment software. Since the true size of the phantom distances do not change and the power and gain of the scanner is kept constant, any change in the measured distances indicates a performance change in the ultrasound system that will be corrected. Results of these measurements are plotted and monitored for drift.
- 2) Phantom images obtained from the RMI 404 GS LE, Small Parts Gray Scale-Attenuation coefficients of 0.7 db/cm/MHz scanning test are evaluated before the project initiates. Subsequently, phantom scanning tests are required every 6 months to assure image quality, image resolution and measurement accuracy (see above) as well as to standardize calibration pixel size for IMT and diameter measurements. In addition, if ultrasound equipment requires replacement or repair (beyond usual maintenance), a phantom scanning test is required.
- 3) Phantom scan procedures:

A) Fill the water dam on the top of the phantom equipment. Ensure that water temperature is between 70-76°F.

B) Set ultrasound equipment image depth to 38 mm. Use the same transducer that is used for the CIMT project. Set the probe's frequency range to the same range as is set for the CIMT project. For example, if in the CIMT project the linear probe is set to 7.0 MHz, then in the phantom scanning test the transducer is set to 7.0 MHz. Likewise, if in the CIMT project the linear transducer is set to 7.5 MHz, then in the phantom scanning test the transducer is set to 7.5 MHz.

[figure not shown]
C) Acquire an image that has 4 horizontal pins and 4 curved-down pins. Set gain as low as possible. Obtain the best axial and lateral resolution for the target group. Capture a digital video clip.

D) Acquire an image that has 4 horizontal pins and 6 vertical pins. Adjust transducer pressure to obtain all pins in the normal positions of the horizontal and vertical lines. Move the focal zone slowly down the imaging field. Set gain as low as possible. The image background must be as dark as possible to display sharper horizontal and vertical pins. Bright background and blurred pins are not acceptable for the calibration procedure. Capture the best digital video image two times.

[figure not shown]
E) Acquire a transverse view of the vessel simulation image by adjusting the imaging gain. Turn the transducer 90° to get a vessel simulation image with optimal gain in the longitudinal view. Capture a digital video clip.

F) Freeze image and measure vessel simulation diameter that is approximately 3.5 mm long. Capture the best digital image.

G) Unfreeze the image to obtain the original vessel simulation image with optimal gain. Then change time gain to maximum. Capture the best digital video image. Change time gain to minimum. Capture the best digital video image.

- H) Complete the phantom work sheet.
- I) Provide 6 video clips for each phantom test:

- 1 video clip - Image that has 4 horizontal pins and 4 curved-down pins
- 2 video clips - Image that has 4 horizontal pins and 6 vertical pins
- 1 video clip - Longitudinal vessel simulation image with optimal gain
- 1 video clip - Longitudinal vessel simulation image with maximum gain
- 1 video clip - Longitudinal vessel image with minimum gain

8.8 Data Security

To assure security of data, processed images are stored electronically and maintained in locked facilities.

8.9 Data Transfer

Participant records are exported to Excel-readable files. Data are down-loaded into an Excel file and delivered to the DCC.

9.2 Laboratory Data

Because the study is double-blinded, all laboratory data except Quest safety data (chemistry, CBC with platelets, PT, aPTT and fibrinogen) will be entered by laboratory personnel directly into the trial data system; clinic personnel will be blinded to these laboratory data. Pre-randomization screening values for LDL-C will be made available to the study clinic personnel. On-trial LDL-C levels will also be routinely reported to the clinic.

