1.5 Exclusion Criteria

- (1) Clinical signs, symptoms, or personal history of CVD
- (2) Diabetes mellitus or fasting serum glucose >140 mg/dL
- (3) Plasma triglyceride levels ≥ 500 mg/dL
- (4) Uncontrolled hypertension (systolic blood pressure >160 mmHg or diastolic blood pressure >110 mmHg)*
- (5) Uncontrolled tachycardia or irregular heart rates (i.e., atrial fibrillation)
- (6) Thyroid disease (untreated)
- (7) Renal insufficiency (defined as serum creatinine >2.0 mg/dL)
- (8) Life threatening illness with prognosis <5 years
- (9) Current use of lipid-lowering medication
- (10) Current use of food supplements containing soy, soy protein, isoflavones or other phytoestrogens
- (11) Known sensitivity or allergy to soy or nuts
- (12) Regular aspirin or other antiplatelet medication use
- (13) Use of anticoagulants
- (14) Bleeding diatheses or tendencies

*Participants who enter screening with a systolic blood pressure >160 mmHg or diastolic blood pressure >110 mmHg will be immediately referred to their physician or to an emergency room. Once the blood pressure is controlled, the participant will become eligible for the trial. Participants who enter screening with mild to moderate hypertension (systolic blood pressure ≤ 160 mmHg or diastolic blood pressure ≤ 110 mmHg) will be notified immediately and a letter issued to the participant and to the participant's physician. Control of hypertension is a requisite to continue into the trial.

1.6

Trial Clinic Flow

- Fasting blood samples drawn for:
 - Chemistry (FSG \leq 140 mg/dL; serum creatinine \leq 2.0 mg/dL)
 - CBC
 - Platelet count
 - Prothrombin time (PT)
 - activated partial thromboplastin time (aPTT)
 - Lipids (triglycerides $<$ 500 mg/dL)
 - C-reactive protein (CRP)
 - Hemoglobin A1c

Draw and store at -80°C (analyze only when eligible):

- Insulin
- Inflammatory markers
 - MCP-1
 - IL-8
 - TNF α
 - IL-1 β
 - IL-10
 - E-Selectin
 - P-Selectin

↓

↓

Schedule randomization visit appointment

8 hour fast

↓

[figure not shown]
↓

Final Eligibility

- Final Eligibility Check List **[Form 17]**
 - ↓
 - ↓

Randomization Visit (v00)

- Nonstudy Medications Record **[Forms 13,14]**
- History of Vitamin and Nutritional Supplement Use Questionnaire **[Form 15]**
- Dietary Food Frequency **[Form 18]**
- Soy Food Questionnaire **[Form 19]**
- 7-Day Physical Activity Questionnaire **[Form 20]**
- Center for Epidemiologic Studies Depression (CES-D) Scale **[Form 21]**
- Cognitive assessment **[Form 22]**

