9.2.2.6 DCC Responsibilities

- 1) Review newly entered laboratory data for completeness and apparent accuracy.
- 2) Perform double data entry on random 10% of laboratory data. Compare double-entered files (entered at laboratory versus DCC). Calculate and report error rates in weekly data reports. Report unacceptably high error rates to Steering Committee.
- 3) Monitor timeliness of entry of data into trial data system.
- 4) Routinely inform laboratory of data not yet entered.
- 5) Compare participant's data with past data for possible within-subject outliers; generate queries to laboratory and monitor responses.
- 6) Monitor possible drift in laboratory values over time.
- 7) Inform laboratory director and laboratory personnel of outliers and data drift in weekly reports.

- 8) Edit database as appropriate in response to data queries.

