9.2.6 Quest Laboratory

Chemistry panel, insulin, CBC, platelet count, PT, aPTT and fibrinogen data are analyzed by Quest. Because these laboratory results constitute clinical safety data are not crucial to blinding of study personnel, these data are transmitted directly from Quest to the study clinic. At the time of receipt, a

photocopy of the laboratory results is made and sent to the DCC.

The contact person in this laboratory is:

[name] [contact]

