9.5.2.4 Participant Safety and Adverse Events

For the EDSMB, the DCC will generate a safety report enumerating the following events, both on a cumulative basis (from the start of the study to present) and new events in the past year. For the EDSMB, adverse events will be presented by blinded study group.

- 1) Laboratory chemistry values out of range (enumerating abnormally low and high values separately). This will be separately reported for first time versus repeated abnormalities.
- 2) Triglycerides >500 mg/dL. First time versus repeated elevations will be separately reported.
- 3) Out of range coagulation and hemostatic factors, PT, aPTT, fibrinogen and platelet count (enumerating abnormally low and high values separately). This will be separately reported for first time versus repeated abnormalities.
- 4) Abnormal bleeding events ascertained from the Bleeding Assessment Questionnaire [**FORMS 6a, 6b**].
- 5) Abnormal urine dipstick.
- 6) Major cardiovascular events: fatal/nonfatal MI, sudden coronary death, hospitalization for unstable angina, and revascularization procedures (CABG and PTCA).
- 7) Major cerebrovascular events: TIA, RIND, CVA.
- 8) Peripheral vascular events including surgical reconstruction and bypass.
- 9) Deep vein thrombosis
- 10) Pulmonary thromboembolism

- 11) Cancers
- 12) Deaths
- 13) Other adverse events; serious and non-serious

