9.5.2.5 Screening and On-Trial Lipid Levels

As each participant completes all screening visits, clinic personnel will use the trial data system to generate a report of lipid levels. On-trial LDL-C levels will also be generated as needed from the trial data system by clinic personnel.

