9.5.3.3 Quality Control

Quality control of the data will include the following:

- 1) Clinical databases:
 - a) Clinic coordinator to review all study forms for completeness and accuracy prior to sending to DCC.
 - b) Study programmers and data clerk to review all data forms for completeness and accuracy prior to data entry.
 - c) Run error check routines on newly entered data. These programs will identify logical errors in the data, missing data, out-of-range or implausible values, and data outliers (both within a given visit and in comparison to a subject's earlier visits).

- d) Based on b and c above, generate data queries in the trial data system to the appropriate study personnel.
- e) Monitor resolution and completeness of responses to data queries.
- f) Edit databases.

2) Laboratory and end point data:

- a) Monitor measures for any apparent longitudinal data drift.
- b) Monitor timeliness of receipt of laboratory data and end point data and identify outstanding laboratory samples.
- c) Perform error check programs and data queries as in section 1 above.
- d) Edit databases.

3) Generate routine quality control reports that will include reporting (by study month) of the numbers of errors in completion of study forms, by form, as well as timeliness and completeness of response to data queries.

4) Monitor study for protocol violations.

5) Double entry of random key study data for monitoring of key stroke error rate.

6) Biannual audit of random data sample for comparison of hard copies to complementary databases.

7) Inform Data Safety Monitoring Board and principal investigator of ongoing/repeated irregularities in any study data.

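### Section 6.1 promises notification of laboratory abnormalities, but the blinding rule in 9.2 leaves it no way to operate for an on-trial triglyceride above 500 mg/dL

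*Combined protocol and SAP*

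**What the plan says.** The plan treats 500 mg/dL as a safety-relevant level twice. At entry, 1.5 excludes "Plasma triglyceride levels ≥ 500 mg/dL". On-trial, 9.5.2.4 lists for the EDSMB report: "Triglycerides >500 mg/dL. First time versus repeated elevations will be separately reported".

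Section 6.1 gives the general rule. Laboratory abnormalities found at the study's research clinic go at once to the principal investigator and, if the participant agrees, to the private physician. Its closing sentence has abnormalities that need referral recorded in the clinic chart, without limiting where they were found.

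Section 9.2 governs who sees which results. Apart from the Quest safety tests, laboratory staff enter results straight into the trial data system, and "clinic personnel will be blinded to these laboratory data". The one on-trial lipid exception is LDL-C, and 9.5.2.5 matches it: "On-trial LDL-C levels will also be generated as needed from the trial data system by clinic personnel". The wider report of lipid levels in 9.5.2.5 is tied to the end of screening.

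Quest results go to the clinic, and 9.2.6 gives the reason: "Because these laboratory results constitute clinical safety data are not crucial to blinding of study personnel".

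**The concern.** A named safety value is withheld, by an explicit rule, from the clinic staff through whom 6.1 would work. For a Quest result the plan builds a full chain: the clinic reviews it, reports it, logs it as an adverse event, and the data coordinating centre (DCC) confirms the logging. For a triglyceride above 500 mg/dL drawn at the same visit, none of these steps is written.

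The stake is individual care. A participant whose triglycerides rise above 500 could wait six months for the next draw, or finish at v36 with no further draw, without the trial telling the investigator or the participant's physician of a result that it already holds.

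**Working it through.** No figure in the plan needs reproducing. The check is a trace of one on-trial triglyceride result, followed by a count of the results under the rule.

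**Trace**

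1. *Source.* Triglycerides are measured by the Core Lipid Laboratory (9.2.2 and 9.2.2.2). They are not among the Quest analytes (9.2.6.2), so the clinic has no second source.
2. *Entry.* Core Lipid staff enter the value directly into the trial data system (9.2.2.1). Section 9.2 blinds the clinic to it; 9.2 and 9.5.2.5 release LDL-C only.
3. *DCC checks on individual values.* These exist. Section 9.2.2.6 says: "Compare participant's data with past data for possible within-subject outliers; generate queries to laboratory and monitor responses". Section 9.5.3.3 screens for "missing data, out-of-range or implausible values, and data outliers" and has the DCC "generate data queries in the trial data system to the appropriate study personnel". Both check whether a number is right. Neither tells anyone to act clinically on a number that is right.
4. *EDSMB.* The board receives summary tables by blinded group (9.5.2.4, 9.6.6), which is not a route to an individual's physician.
5. *Adverse-event logging.* Entering abnormal laboratory values on the log is a clinic duty in 9.2.6.4 (item 9), and the DCC confirms it in 9.2.6.7 (item 9). Both stand in the Quest section. The matching Core Lipid sections (9.2.2.4 to 9.2.2.6) contain neither duty.
6. *LDL-C as an indirect signal.* Above 500 mg/dL, 9.2.2.2 sets the calculated LDL-C to missing, and 7.11.24 has LDL-C measured directly. A blank might hint at the cause, but nothing tells the clinic to read it that way. If the direct value is what the clinic sees, there is no blank.

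The trace ends without a step that carries the individual value to the clinic, the investigator or the physician.

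**Count of results under the rule**

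Inputs: on-trial lipid visits v06, v12, v18, v24, v30 and v36 (9.2.2.3), so 6; planned sample size 240 (1.3); full attendance assumed.

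- All scheduled results: 6 × 240 = 1,440
- With a next draw six months later (v06 to v30): 5 × 240 = 1,200
- With no later draw (v36): 240, and 240 / 1,440 = 16.7%

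These are scheduled results, not abnormal ones. The documents give no rate above 500 mg/dL. As an assumption only:

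| Assumed share above 500 | v06 to v30 | v36 | Total |
|---|---|---|---|
| 0.1% | 1.2 | 0.24 | 1.44 |
| 1% | 12 | 2.4 | 14.4 |

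The rate is probably low, because everyone enters below 500.

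**The case against.** The best case for the plan is that 6.1 already covers this. Its closing sentence is not restricted to findings made at the clinic, and the Core Lipid Laboratory belongs to the same research unit. Section 9.2 blinds clinic personnel and does not say that the principal investigator may not be told. Much of this stands. A reader might infer that the plan has no participant-level route at all; the documents do not support that, because the principle is written down. What is missing is the step that delivers this value to someone who can apply it.

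Section 9.5.2.4 also lists the value under adverse events, and 6.12.1 has reportable adverse events discussed with the principal investigator. That is a partial route: it is limited to serious events and to unexpected events possibly related to the intervention, and it presupposes that someone has logged the event. The notice to the principal investigator in 9.5.3.3 (item 7) concerns irregularities in data, which is a quality-control matter.

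Withholding research-laboratory results is a deliberate masking choice, and a sound one in general. But LDL-C is already released, and the visible text does not say why the reasoning that frees Quest safety data stops short of a triglyceride above 500.

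Finally, parts of the document were not available to this review, including pages just before 9.2 and under the organizational structure. An alert route could sit there. This limits the point to the visible text.

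**Conclusion.** The point holds as a gap in delivery: followed as written, 9.2 keeps a named safety value from the people who would act under 6.1. It is a minor issue with a cheap remedy. It rests on the visible text and on reading the queries in 9.2.2.6 and 9.5.3.3 as data-quality checks. The number of affected results is unknown; the range of about 1 to 14 depends wholly on the assumed 0.1% to 1%.

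Several stronger inferences should not be drawn.

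- *That 500 mg/dL is an on-trial stopping or action limit.* It is an entry criterion and a reporting item; no visible text makes it more.
- *That the treatment comparison is biased.* The rule is the same in both arms, and the EDSMB tables still count these values.
- *That 7.11.24 and 9.2.2.2 contradict each other.* The first provides for direct measurement; the second blanks only the calculated LDL-C. Both can hold.
- *That affected participants would go unnoticed.* Section 6.1 keeps them in their usual medical care, which may find the abnormality independently. The documents describe no consequence of a late notice.

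**What to change.** In 9.2 and 9.5.2.5, state that any on-trial triglyceride above 500 mg/dL, including one at v36, is released to the clinic with the LDL-C report, and that notification under 6.1 and adverse-event logging as in 9.2.6.4 (item 9) then apply. If an alert route already exists in another section, a cross-reference in 9.2 is enough. The clinical response remains for the investigators to set.

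The cost is about two sentences and one conditional field in a report that the clinic already generates. The loss of masking is negligible, since LDL-C is already released and triglycerides at or below 500 stay masked.

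As separate housekeeping, a field for directly measured LDL-C could be added to the data list in 9.2.2.2.

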9.2.1 Sample Labeling and Tracking

Bar-code labeling will be used for collection, processing, storage and disposition of all laboratory samples by the following procedure:

- 1) The samples to be collected at each clinic visit will be listed in pre-made requisition forms, generated through the trial data system; the requisition form will contain pre-printed participant ID, visit number (linking visit number to samples to be collected), number and type of blood tubes to be used for that particular clinic visit and a bar code.
- 2) Sample collection tube labels will be generated at the study clinic using the trial data system. On the initial collection tubes, labels will include participant ID, visit number and the type of tube and specimen collected, thus assuring that the proper sample is collected in the appropriate collection tube for each clinic visit.
- 3) Receipt of samples by staff at the Core Lipid Laboratory will be compared and verified against the bar-coded laboratory requisition form that shows which samples should be received according to clinic visit. Any missing samples will be immediately brought to the attention of the clinic staff.
- 4) The Core Lipid Laboratory staff will use the trial data system to generate bar-coded labels (cryolabels for stored samples) for each tube. The bar code will contain data on participant ID, visit number, type of sample collected and a laboratory ID number.
- 5) In addition to the data included in the bar code, the sample data table in the trial database will include date of sample collection, the directed analyte(s) for future measurements of stored samples, storage location (for stored samples), as well as information on ultimate disposition and receipt of the sample (date sent, date received, to what laboratory, comments), thereby serving as the laboratory log as to the receipt and disposition of all samples.
- 6) A sample flow-sheet that shows the number and type of samples to be stored at -80°C will be used by Core Lipid Laboratory staff to compare and verify against the pre-made requisition forms for each clinic visit.
- 7) Personnel from the following laboratories will enter their respective laboratory measurements directly into the sample data table: Core Lipid Laboratory, Hematology Laboratory, Rheology Laboratory, Biochemistry Laboratory.

8) The DCC will run routine checks of the laboratory data tables to determine whether and which data may be missing. If data are missing because of shipment loss or sample loss at the laboratory level, back-up storage samples will be re-shipped to the appropriate laboratory so that the analyte can be measured.

9.2.2 Lipid, C-Reactive Protein (CRP) and Hemoglobin A1c Data

Samples will be analyzed by the ARU Core Lipid Laboratory to obtain lipid, CRP and hemoglobin A1c data. The contact person at this laboratory is:

[name], [contact] or [contact], [contact]

9.2.2.1 Data Transmission

All data will be entered directly into the trial data system by personnel at the Core Lipid Laboratory. A random sample of hard copies of data will be requested by the DCC for double entry and estimation and monitoring of data entry error rates.

9.2.2.2 Study Data

The following data will be obtained:

A) Lipids (precipitation method):

- 1) total plasma cholesterol
- 2) total plasma triglycerides
- 3) plasma HDL-C
- 4) calculated VLDL-C
- 5) calculated LDL-C

LDL-C will be calculated by the Friedewald equation:

$$\text{LDL} = \text{Total Cholesterol} - \text{HDL-cholesterol} - (\text{Triglycerides}/5)$$

This equation is applicable only when triglycerides are less than 500 mg/dl. When triglycerides are greater than this value, the calculated LDL-C will be set to missing in the lipid database. Calculated LDL-C and VLDL-C (Triglycerides/5) will be computed by the DCC after data entry of laboratory lipids.

B) Metabolic

- 6) C-reactive protein
- 7) hemoglobin A1c

9.2.2.3 Data Collection Schedule

- 1) Lipid data by the precipitation method will be assessed at the screening visit (SV) and v06 and every 6 months on-trial (study visits v12, v18, v24, v30, v36).
- 2) CRP will be assessed at the screening visit (SV) and v06 and every 6 months on-trial (study visits

v12, v18, v24, v30, v36).

- 3) Hemoglobin A1c will be obtained at SV, v03 and v06 and every 6 months on-trial (study visits v12, v18, v24, v30 and v36).

